9.4 STATISTICAL ANALYSES

The statistical analysis plan will be finalized prior to database lock or any interim analysis and it will include a more technical and detailed description of the statistical analyses described in this section. A specific dedicated SAP might be produced in addition to the main SAP, eg, for some or all biomarker analyses. This section is an overview of the planned exploratory statistical analyses of the most important endpoints including primary and key secondary endpoints.

9.4.1 Participant description

9.4.1.1 *Disposition of participants*

A detailed description of participant accountability including count of participants by analysis populations ([Table 3](#)), screen failure participants with reasons for screen failure, participants who did not complete the study observation period along with the main reason for permanent treatment discontinuation, and participants who requested permanent treatment discontinuation, will be generated by study groups.

All withdrawals from the study, taking place on or after study intervention intake, will be fully documented in the body of the clinical study report (CSR).

A listing of subjects with treatment discontinuation will be provided.

9.4.2 Protocol deviations

During the review of the database, compliance with the protocol will be examined with regard to inclusion and exclusion criteria, treatment compliance, prohibited therapies, and timing and availability of planned assessments. A pre-defined list of potential protocol deviations will be identified by the study team prior to the study start. The protocol deviations will then be reviewed by the study team before database lock, including missing data and study drug discontinuations, and classified as critical, major, or minor deviations.

Individual deviations to inclusion and exclusion criteria as reported by the Investigator will be listed.

If any major and critical deviations other than those involving inclusion/exclusion will be listed by participant and/or described in the body of the CSR.

9.4.3 Demographic and baseline characteristics

9.4.3.1 Participant demographic characteristics, medical history, and diagnoses

Continuous variables (age, weight) and qualitative variables (gender, race, and body mass index [BMI]) will be summarized by study groups, by descriptive statistics (summary tables) for the modified intent-to-treat (mITT) population and for additional population if relevant (eg, if many participants from the mITT population are not part of the safety population).

Specific medical/surgical history will be listed. Other baseline characteristics will be listed.

Disease characteristics at baseline: eg, ClinRO and PROs will be presented along with the on-treatment summary statistics in the [Section 9.4.6](#).

9.4.3.2 Baseline efficacy parameters

Baseline is defined as the last available and evaluable value before and closest to the first dose of the IMP ie, at Day 1 (Visit 2, Week 1), for AD participants and as the last available and evaluable value at Screening or Day 1 (Visit 2) for healthy participants.

9.4.3.3 Baseline safety parameters

Baseline for safety parameters will be defined as the last available and evaluable value before and closest to the first dose of IMP for patients and as the last available and evaluable value at screening for healthy participants.

Baseline safety values will be presented along with subsequent safety values assessed during the study.

9.4.4 Extent of study treatment exposure and compliance

The extent of study treatment exposure and compliance will be assessed and summarized for patient group within the safety population.

The following listings will be provided:

- Patients receiving IMP from specified batch; (patient, IMP, and IMP batch number) will be sorted by patient.

9.4.4.1 Extent of investigational medicinal product exposure

Duration of IMP exposure is defined as: last dose date – first dose date + 14 days, regardless of unplanned intermittent discontinuations.

If the patient's date of last dose is unknown, his/her last IMP dispensing date will be used in its place.

Duration of exposure will be summarized in patients' group using descriptive statistics such as mean, standard deviation (SD), median, minimum and maximum.

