| Section 1.1 Synopsis | 
Changed “2 to 4 weeks” to “up to 4 weeks”
 
Screening Period: up to 4 weeks before inclusion. 
Changed “21 weeks” to “20 weeks”
 
Total duration of Observation Period: up to 20 weeks. | To keep consistent with the schedules in Section 1.3. |
| Section 1.2 SCHEMA | 
Changed Week 2 to Week 3, Week 16 to Week 17, and Week 20 to Week 21 in the graphical study design.
 
Changed “N=40” to “34 AD participants”.
 | To keep consistent with the schedules in Section 1.3 and study population in Section 5. |
| Section 1.3 Schedule of activities (SOA)-AD participants | Added an annotation g to Non-lesional skin sample collection at baseline to indicate this biopsy is optional. | To keep consistent with the skin biopsy sample collection procedures in Section 8.3.1. |
| Section 1.3 Schedule of activities (SOA)-AD participants | Removed IMP dispense from Visit 5. | To correct a discrepancy, no IMP dispense is planned at EOT visit |
| Section 1.3 Schedule of activities (SOA)-AD participants | 
Added a footnote j to archival blood sample collection:
 
Whole blood sample collected at baseline and stored during the study for potential analysis if deemed necessary for safety reasons. Will be described in study reference manual.
 
The subsequent footnote numbers were updated accordingly.
 | To clarify the purpose of the archival blood sample collection |
| Section 1.3 Schedule of activities (SOA)-AD participants and Section 8.4.2 Vital signs | Removed pulse rate from Section 1.3 and removed both pulse rate and respiratory rate from vital sign parameters in Section 8.4.2. | To correct a discrepancy, heart rate is already part of vital signs, and respiratory rate is not planned/relevant for this study |
| Section 4.1 overall design | 
Change 28 days to 21 days:
 
Healthy participants will undergo a Screening Period of 21 days and a 7 days Observational Period following collection of the skin biopsy.
 | To keep consistency with Section 1.4 |

| Section # and Name | Description of Change | Brief Rationale |
|--|--|---|

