1.3 SCHEDULE OF ACTIVITIES (SOA) - AD PARTICIPANTS

| Phase | Screening | Treatment period | | | | | | | | | | Follow-up | |
|---|-------------|------------------|----|----------------|----------------|-----|----------------|----------------|----------------|----------------|----------------|----------------|------|
| | | D1 | D8 | D15 | D29 | D43 | D57 | D71 | D85 | D99 | D113 | D141 | D197 |
| Day | D-28 to D-1 | | | | | | | | | | | | |
| Week | W-4 to W0 | W1 | W2 | W3 | W5 | W7 | W9 | W11 | W13 | W15 | W17 (EoT) | W21 (EoS) | W29 |
| Visit | 1 | 2 ^a | | 3 | | 4 | | | | | 5 ^b | 6 | |
| Informed consent | X | | | | | | | | | | | | |
| Visit at clinical site | X | X | | X | | X | | | | | X | X | |
| Telephone call | | | | | | | | | | | | | X |
| Inclusion/exclusion criteria | X | X | | | | | | | | | | | |
| Demographics | X | | | | | | | | | | | | |
| Medical/surgical history | X | | | | | | | | | | | | |
| Prior/concomitant medications | | | | | | | X | | | | | | |
| eDiary ^c | | | | | | | | X | | | | | |
| Training for IMP administration and PRO assessments | | X | | X | | | | | | | | | |
| Blood sample ^d | | X ^a | | | | | | | | | X | X | |
| Skin biopsy^e | | | | | | | | | | | | | |
| Pruritic lesional skin | | X ^a | | | | | | | | | | | |
| Matched post-lesional healed, non-pruritic non-lesional skin ^f | | | | X ^g | | | | | | | X | X ^g | |
| Non-lesional skin ^g | | X ^{a,g} | | | | | | | | | | | |
| IMP | | | | | | | | | | | | | |
| Dupilumab administration ^h | | X | | X | X ⁱ | X | X ⁱ | X ⁱ | X ⁱ | X ⁱ | | | |
| IMP dispense | | X | | X | | X | | | | | | | |

| Phase | Screening | Treatment period | | | | | | | | | | Follow-up | |
|--|-------------|------------------|----|-----|-----|-----|-----|-----|-----|-----|----------------|-----------|-----|
| | | D1 | D8 | D15 | D29 | D43 | D57 | D71 | D85 | D99 | D113 | | |
| Day | D-28 to D-1 | | | | | | | | | | | | |
| Week | W-4 to W0 | W1 | W2 | W3 | W5 | W7 | W9 | W11 | W13 | W15 | W17 (EoT) | W21 (EoS) | W29 |
| Visit | 1 | 2 ^a | | 3 | | 4 | | | | | 5 ^b | 6 | |
| IMP accountability and compliance check | | | | X | | X | | | | | X | | |
| Safety | | | | | | | | | | | | | |
| Physical examination | X | X ^a | | | | | | | | | | X | |
| Height | | X ^a | | | | | | | | | | | |
| Body weight | | X ^a | | | | | | | | | | | |
| Archival blood sample ^j | | X ^a | | | | | | | | | | | |
| Serology tests | X | | | | | | | | | | | | |
| Vital signs ^k | X | X ^a | | | | X | | | | | X | X | |

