- b Participants who discontinue the study treatment prematurely the end of treatment (EoT) assessments will be performed at the time of discontinuation to assure a complete clinical assessment in close temporal proximity to the premature termination of study treatment. In addition, to allow assessment of participant outcomes over the stipulated study period, participants will be asked and encouraged to complete all remaining study visits and participate in all assessments according to the visit schedule.
- c Electronic diary will be dispensed to the patients at Screening Visit (V1) and will be collected on Week 21 (Visit 6). The PROs will be administered to patients via eDiary. Patients will bring the eDiary to the site at each visit, and it will be reviewed and dispensed back to patients at each visit.
- d For future use and exploratory research; collection is optional; whole blood sample for DNA extraction will be collected at baseline only.
- e Biopsy (4 mm). Skin biopsy in AD participants will be collected in lesional tissue, with acute lesions. Excluding oozing, infections and chronic stages - lichenification. Preferably in the forearms followed by back.
- f Post-lesional healed or healing skin should localisation matched to the baseline pruritic lesional biopsy; if post-lesional healed skin that is completely non-pruritic non-lesional is not available at later visits, one of the following biopsies should be collected (in the order of relevance): 1. lesional non-pruritic skin, 2. Post-lesional pruritic skin or 3. lesional pruritic skin
- g Optional.
- h The IMP will be administered every 14 ± 2 days (Q2W) during the 16-week treatment period.
- i Self administration by AD patients or caregivers at home.
- j Whole blood sample collected at baseline and stored during the study for potential analysis if deemed necessary for safety reasons. Will be described in study reference manual.
- k Vital signs, including heart rate, systolic and diastolic blood pressure (mmHg), and body temperature (°C) will be measured.
- l Urine pregnancy test could be performed at home with or without the assistance of a home care provider. In case of positive urine test the study treatment will be withheld and a serum pregnancy test should be performed as soon as possible, to confirm the pregnancy. Pregnancy will lead to definitive treatment discontinuation in all cases.
- m Participants self assessment.

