6.1 STUDY INTERVENTION(S) ADMINISTERED

Study participants will be assigned to study intervention as described below:

- Up to 34 patients with moderate-to-severe AD will receive dupilumab.
 - Dose regimen: Participants will receive a SC loading dose of dupilumab 600 mg on Day 1, followed by Q2W SC dosing of dupilumab 300 mg (2 mL of a 150 mg/mL solution) from Week 3 to Week 15.

One kit number list is generated centrally by Sanofi and IMP is packaged in accordance with this list.

Study intervention will be dispensed at the study visits summarized in SoA (see [Section 1.3](#)). Returned study intervention should not be re-dispensed to the participants.

Table 2 - Overview of study interventions administered

| | |
|--|---|
| ARM name | Dupilumab |
| Intervention name | Dupilumab 300 mg |
| Type | Biological |
| Dose formulation | A 150 mg/mL dupilumab solution in a prefilled syringe to deliver 300 mg in 2 mL |
| Unit dose strength(s) | 300 mg |
| Dosage level(s) | 300 mg every 14 ±2 days after an initial loading dose of 600 mg |
| Route of administration | Subcutaneous ^a |
| Use | Experimental |
| IMP | IMP |
| Packaging and labeling | Each dose of dupilumab will be supplied as 1 glass prefilled syringe packed in a patient kit box. Both glass prefilled syringe and the box will be labeled as required per country requirement. |
| Storage | 2°C to 8°C |
| Current/Former name(s) or alias(es) | Dupixent |

^a Subcutaneous injection sites should alternate between the upper thighs, 4 quadrants of the abdomen, or the upper arms, so that the same site is not injected twice during consecutive administrations. Injection in the upper arms can only be done by the study site staff and/or by a trained person or health care professional but not the participant themselves. Site of injection should be locally distant from the site of skin biopsies.

Investigational medicinal product

The IMP will be administered every 14 ± 2 days (Q2W) during the 16-week treatment period (with the last IMP administration at Week 15).

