9.4.4.2 Compliance

A given administration will be considered noncompliant if the patient did not take the planned dose of treatment as required by the protocol. No imputation will be made for patients with missing or incomplete data.

Percentage of compliance for a patient will be defined as the number of administrations the patient was compliant divided by the total number of administrations the patient was planned to take (the number of doses missed due to interruptions at Investigator's judgment will not be subtracted) on or before the last IMP administration date.

Treatment compliance, above-planned and under-planned dosing percentages will be summarized descriptively (N, mean, SD, median, minimum, and maximum). The percentage of patients with compliance <80% will be summarized. In addition, number and percentage of patients with at least 1 above-planned dosing administration will be given, as well as the number and percentage of patients with 0, (0, 20%), and >20% under-planned dosing administrations.

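### When the last dose date is unknown, exposure is dated from the last dispensing visit (D43 on schedule), which halves it for a participant who dosed at home through D99

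*Protocol*

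**What the plan says.** Protocol Section 9.4.4.1 gives the formula: "Duration of IMP exposure is defined as: last dose date – first dose date + 14 days, regardless of unplanned intermittent discontinuations". For a missing end date it gives one fallback: "If the patient's date of last dose is unknown, his/her last IMP dispensing date will be used in its place".

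The schedule of activities (Protocol Section 1.3) sets the dates. Its day columns after screening run "D1 | D8 | D15 | D29 | D43 | D57 | D71 | D85 | D99 | D113 | D141 | D197", and the dispensing row reads "IMP dispense | | X | | X | | X", with the three marks under D1, D15 and D43 (Visits 2, 3 and 4). Administration is marked at D1, D15, D29, D43, D57, D71, D85 and D99. The last four of these, and D29, carry the footnote "Self administration by AD patients or caregivers at home". Section 6.1 confirms the end of dosing: "with the last IMP administration at Week 15", which is D99. Section 6.1 also says that interim visits for dispensing may be needed between scheduled visits.

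The SAP lists its departures from the protocol in Section 1.2, and the exposure rule is not among them. Section 1.2.4 only drops the above-planned and under-planned dosing percentages. The general convention in SAP Section 1.3, that missing data are not replaced, yields to whatever the protocol's statistical section says otherwise. The fallback therefore stands.

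**The concern.** A dispensing date marks the start of a supply period. It is a fair stand-in for the last dose only if little dosing follows it. Here the last scheduled dispensing is itself a dosing day, and half of the planned doses come after it. The fallback therefore credits none of the doses for which that last supply was handed out.

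The rule also does not say how it ranks against partial information. If home injections at D57 and D71 are dated and only the final one is not, a literal reading still sets the last dose at D43, earlier than injections known to have been given.

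What is at stake is the exposure summary. It is where a reader checks that about 16 weeks of treatment were delivered. A participant who completed dosing could appear there with 8 weeks. In a study of 34 patients that reports the minimum, mean and SD, a single such record is visible.

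**Working it through.** **Inputs**
- Formula and fallback: Protocol Section 9.4.4.1.
- Dispensing days D1, D15, D43 and dosing days D1 to D99: Protocol Section 1.3.
- Dosing interval 14 ± 2 days and 16-week treatment period: Protocol Section 6.1.
- SAP Section 1.2.2 window for the D99 home dose: 93 to 106 days after the first dose.
- Planned number of AD participants: 34.

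**Step 1. Reproduce the plan's own figure.** All eight doses on schedule: 99 − 1 + 14 = 112 days = 16 weeks. This equals the stated treatment period, so the formula itself is sound.

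**Step 2. Apply the fallback.** With D43 in place of the last dose: 43 − 1 + 14 = 56 days = 8 weeks. Ratio 56/112 = 0.50; shortfall 56 days.

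**Step 3. Check that timing windows do not matter.**
- Every interval 12 days: 3 × 12 + 14 = 50 against 7 × 12 + 14 = 98 (51%).
- Every interval 16 days: 3 × 16 + 14 = 62 against 7 × 16 + 14 = 126 (49%).
- D99 dose anywhere in the SAP window: true exposure 93 + 14 = 107 to 106 + 14 = 120 days, so 56 is 52% to 47% of it.

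**Step 4. Allow for interim dispensing (assumed dates), all doses taken.**

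| Last dispensing | Fallback exposure | Share of 112 days |
|---|---|---|
| D43 (scheduled) | 56 | 50% |
| D57 | 70 | 62.5% |
| D71 | 84 | 75% |
| D85 | 98 | 87.5% |

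**Step 5. Effect on the group summary.** The documents give no frequency for unknown last-dose dates, so the number affected, m, is an assumption. With all others at 112 days, mean = (56m + 112(34 − m))/34.
- m = 1: (56 + 3696)/34 = 110.4 days
- m = 3: (168 + 3472)/34 = 107.1 days
- m = 5: (280 + 3248)/34 = 103.8 days

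In each case the reported minimum becomes 56 days.

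**Step 6. What the latest recorded date would recover.** The same formula gives 70, 84 or 98 days if the last dated injection is D57, D71 or D85. If no home injection after D43 is dated, the latest record is the on-site dose at D43 and the result is still 56 days. Only the syringe count can tell that participant apart from one who stopped.

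**The case against.** The strongest reply is that the situation should be uncommon. Under Protocol Section 6.4, dosing information is entered in the eCRF, unused syringes are counted, and the monitor compares the eCRF with the retrieved product and source documents. The eDiary is reviewed at each visit (Section 1.3, footnote c), and an accountability check falls on D113, 14 days after the last planned dose. The SAP's windows for home doses presuppose recorded dates. This stands. A reader might infer that last-dose dates will mostly be missing, or that the eDiary is the only record of home doses; the documents contradict the second and give no support to the first.

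A reader might also infer that the compliance denominator falls from eight planned doses to four, because Section 9.4.4.2 counts planned administrations "will not be subtracted) on or before the last IMP administration date". That is not established. The substitution is written only into the exposure definition, and Section 9.4.4.2 rules out imputation for missing or incomplete data. It does not say which date then closes the denominator, but that is a separate gap.

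Nor is the primary result at risk. Exposure is summarised in the safety population (Section 9.4.4). The primary analysis uses the mITT population, which has no exposure criterion, and no formal testing is planned. Treatment discontinuations are reported and listed separately (Section 9.4.1.1), so a reader could see that the participant was not recorded as having stopped.

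Two further replies are fair. If the participant really stopped after D43, 56 days is correct, and a rule that credits no undocumented doses is a defensible conservative convention. And the fallback may have been meant only for participants with no usable date at all, in which case recorded later injections would take precedence; the text does not say so.

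Finally, the amendment log entry "Removed IMP dispense from Visit 5" might suggest that Amendment 01 caused the gap. It did not: Visit 5 is D113, after the last dose.

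**Conclusion.** The point holds as a minor defect in a stated rule. For a participant who took every dose, has no last-dose date and was last supplied at D43, exposure is reported as 56 days instead of 112. That size rests on full dosing and on no interim dispensing; it shrinks with later dispensing and is zero for a true stop after D43. The claim that recorded later injections could be overridden rests on a literal reading of an ambiguous sentence.

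The frequency is unknown and probably low. One affected participant moves the mean by 112 − 110.4 = 1.6 days, and the more noticeable effect is on the minimum. The consequence is confined to the descriptive exposure summary. No effect on compliance percentages or on the efficacy analyses is shown.

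**What to change.** In Protocol Section 9.4.4.1, and in the SAP as a listed change, replace the dispensing-date fallback. When the last dose date is unknown, use the latest administration date recorded in the eCRF or eDiary, including on-site doses, and flag the imputed date in the listing.

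As an optional sensitivity summary, use the scheduled date of the last dose that the syringe count supports, capped at the EoT or discontinuation date. This covers the participant with no dated injection after D43, whom the main rule would still leave at 56 days.

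The cost is a sentence or two of text and slight extra programming. The data are already collected: accountability checks are scheduled at D15, D43 and D113. The change concerns analysis only and alters nothing in dosing or dispensing.

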9.4.4.2 Compliance

A given administration will be considered noncompliant if the patient did not take the planned dose of treatment as required by the protocol. No imputation will be made for patients with missing or incomplete data.

Percentage of compliance for a patient will be defined as the number of administrations the patient was compliant divided by the total number of administrations the patient was planned to take (the number of doses missed due to interruptions at Investigator's judgment will not be subtracted) on or before the last IMP administration date.

Treatment compliance, above-planned and under-planned dosing percentages will be summarized descriptively (N, mean, SD, median, minimum, and maximum). The percentage of patients with compliance <80% will be summarized. In addition, number and percentage of patients with at least 1 above-planned dosing administration will be given, as well as the number and percentage of patients with 0, (0, 20%), and >20% under-planned dosing administrations.

9.4.5 Prior/Concomitant medication/therapy

Medications will be coded according to the World Health Organization Drug Dictionary (WHO Drug Dictionary, last available version before database lock). Concomitant medications with the IMP will be listed separately by participants.

9.4.6 Efficacy analyses

The efficacy evaluation will be based upon the review of the individual values (graphics), descriptive statistics (summary tables, graphics) and, where applicable, exploratory statistical analysis.

Due to the small sample size and the exploratory nature of the study, missing, or incomplete data of efficacy marker will not be imputed. In case a significant number of patients (eg, more than 20%) using rescue therapy are observed during the study Treatment Period, visit values removed due to use of rescue therapy will be imputed. The imputation methods applied will be described in the SAP.

